10.2.1.2. Maintenance Period Considerations

For maintenance period efficacy measures, unless otherwise stated, baseline will be the last available value before the initial randomization in the induction period, which in most cases will be the value recorded at Week 0 (Visit 2).

For maintenance period safety measures, unless otherwise stated, baseline will be the last available value before the initial dose in the maintenance period, which in most cases will be the value recorded at Week 16. Additional information on baseline for efficacy and safety analyses will be available in the SAP.

Maintenance phase analyses are exploratory; therefore, only descriptive statistics will be provided. Change from baseline and 95% CI will be calculated by treatment for continuous variables. The proportion and 95% CI will be reported by treatment for categorical variables.

Additional sensitivity analyses for the primary and key secondary endpoints may be done and will be specified in the SAP.

10.2.2. Treatment Group Comparability

10.2.2.1. Subject Disposition

All subjects who discontinue from the study or the study treatment will be identified, along with their reason for discontinuation. Reasons for discontinuation from the study will be summarized by treatment group.

10.2.2.2. Subject Characteristics

Demographic and baseline characteristics will be summarized descriptively by treatment group. Descriptive statistics including number of subjects, mean, standard deviation, median, minimum, and maximum will be provided for continuous measures, and frequency counts and percentages will be tabulated for categorical measures.

10.2.2.3. Concomitant Therapy

Concomitant medications will be summarized for subjects who enter each treatment period and will be presented by anatomical therapeutic chemical drug classes using the latest version of the WHO drug dictionary.

10.2.2.4. Treatment Compliance

Treatment compliance with IP will be summarized for subjects who enter the Induction and Maintenance periods. A subject will be considered as having missed the visit if he or she fails to attend for administration of the IP within the required treatment window as defined in the Schedule of Activities (Section 2). Overall compliance with therapy is defined to be missing no more than 20% of the expected doses within the protocol-defined dosing interval and not missing 2 consecutive doses. The proportion of subjects who demonstrate overall compliance during the Induction Period will be compared between treatment groups using Fisher's exact test.

10.2.3. Efficacy Analyses

10.2.3.1. Primary Analyses

The primary efficacy measure is the binary outcome of response defined as IGA score of 0 or 1 (clear or almost clear skin) and ≥ 2 -point improvement from baseline at Week 16. Primary analysis will be conducted using the previously described logistic regression model.

10.2.3.2. Secondary Analyses

The previously described logistic regression model will be used to analyze the proportion of subjects achieving the following:

- IGA of 0 at Week 16
- EASI-50, EASI-75, and EASI-90 at Week 16, where EASI-75 and EASI-90 are defined as having an improvement of at least 75% and 90% from baseline, respectively.
- SCORAD75 and SCORAD90 at Week 16, where SCORAD75 and SCORAD90 are defined as having an improvement of at least 75% and 90% from baseline, respectively.
- IGA of 0 or 1 at Week 52

The previously described MMRM model will be used to analyze mean change from baseline for:

- EASI score
- SCORAD score

10.2.3.3. Exploratory Analyses

Improvement in signs and symptoms, health outcome measures, and QoL measures (total scores, item scores, and derivations) at each time point collected (induction and maintenance) will be summarized using descriptive statistics and the previously described models for discrete and continuous endpoints. The Kaplan–Meier product limit method will be used to estimate the survival curves for time-to-event variables such as loss of response and maintenance of response.

10.2.4. Safety Analyses

All safety data will be descriptively summarized for the safety population by treatment group and analyzed using the methods described in Section 10.2.1.

Adverse events will be coded according to the Medical Dictionary for Regulatory Activities and summarized by system organ class, preferred term, severity, and relationship to IP. A TEAE is defined as an event that first occurred or worsened in severity after baseline. For each event classification term, the number of subjects experiencing a TEAE with that classification term will be tabulated.

Treatment-related TEAEs are defined as events that are indicated by the investigator on the eCRF to be related to treatment. For events that are gender specific, the denominator and computation of the percentage will include only subjects from the given gender.

10.2.5. Pharmacokinetic/Pharmacodynamic Analyses

Analyses of PK/PD data will be performed using a nonlinear mixed-effect modeling approach as implemented in NONMEM software on a computer that meets or exceeds the minimum system requirements for this program. It is possible that other validated equivalent software programs may be used if appropriate. The version of any software used for the analysis will be documented. Population PK analyses will be performed to characterize the PK of LY3375880. These analyses will include model-based and graphical evaluations of the data. Estimates of PK model parameters and covariate effects and corresponding CIs will be reported. Analyses of exposure–response relationships will be conducted using both exploratory graphical approaches and model-based approaches. Exploratory graphical analysis approaches for categorical clinical endpoints (e.g., IGA, EASI, etc.) may consist of graphs showing the percentage of subjects that achieve the clinical endpoint at different percentiles (e.g., quartiles) of exposure of LY3375880 at Week 16. Measures of exposure may include population PK estimated average steady-state concentrations (Css, avg) or observed trough concentrations at the time of the clinical endpoint. Model-based analyses of the categorical clinical endpoints will utilize population exposure–response logistic regression models, where maximum effect (E_{max}) or other model structures may be used to relate exposure to the probability of achieving the endpoint. These models may be used to evaluate subject factors that may impact the relationship between exposure and the probability of achieving the endpoint. Longitudinal exposure–response models for EASI scores or response rates may be developed, which relate the time course and magnitude of LY3375880 exposure to the time course and magnitude of EASI response.

Exploratory analyses examining the relationships between LY3375880 exposure and PD biomarker responses may be conducted. Additional analyses may be conducted if they are deemed appropriate. Further details on PK and PK/PD analyses will be provided in the PK/PD analysis plan.

10.2.6. Evaluation of Immunogenicity

The frequency and percentage of subjects with preexisting ADA and with TE ADA+ to LY3375880 will be tabulated. TE ADA+ are defined as those with a titer 2-fold (1 dilution) greater than the minimum required dilution if no ADA were detected at baseline (treatment-induced ADA) or those with a 4-fold (2 dilutions) increase in titer compared to baseline if ADA were detected at baseline (treatment-boosted ADA). For the TE ADA+ subjects, time to first TE ADA+ result, distribution of maximum titers, and titer evolution over time will be described. The frequency of neutralizing antibodies will be tabulated in TE ADA+ subjects. The relationship between the presence of antibodies to LY3375880, IL-33 target engagement, PK parameters, efficacy, and safety parameters will be assessed, as well as the potential impact of rechallenge on ADA responses.

10.2.7. Other Analyses

10.2.7.1. Health Economics

The health outcome measures will be analyzed using methods described for continuous or categorical data as described for efficacy measures in Section 9.1.

10.2.7.2. Subgroup Analyses

Subgroup analyses will be conducted for the primary endpoint defined as IGA score of 0 or 1 (clear or almost clear skin) and ≥ 2 -point improvement from baseline at Week 16 using NRI for the ITT Population. Subgroups to be evaluated may include region, age, sex, race, baseline IgE levels, baseline levels of type II immune response analytes, etc.

A logistic regression model with treatment, subgroup, and the interaction of subgroup-by-treatment included as factors will be used. The subgroup-by-treatment interaction will be tested at the significance level of 0.10. If the interaction is statistically significant at $\alpha = 0.10$, the nature of the interaction will be explored.

Definitions for the levels of the subgroup variables, the analysis methodology, and any additional subgroup analyses will be defined in the SAP. This study is not powered for subgroup analyses; therefore, all subgroup analyses will be treated as exploratory.

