10.2. Statistical Analyses

10.2.1. General Statistical Considerations

Statistical analysis of this study will be the responsibility of Lilly or its designee. A detailed SAP describing the statistical methodologies will be developed by Lilly or its designee.

Efficacy analyses will be conducted on the intent-to-treat (ITT) population. This set includes all randomized subjects, even if the subject does not take the assigned treatment, does not receive the correct treatment, or otherwise does not follow the protocol.

Safety analyses will be conducted on the safety population. This set includes all data from all randomized subjects receiving at least 1 dose of the IP according to the treatment to which the subjects were randomized.

When reported, descriptive statistics will include the number of subjects, mean, standard deviation, median, minimum, and maximum for continuous measures, and frequency counts and percentages for categorical measures.

Treatment comparisons of discrete efficacy variables between LY3375880 and placebo will be made using a logistic regression analysis with treatment, baseline disease severity (IGA 3 versus 4), geographic region, and, if applicable, baseline scores (such as baseline EASI score for a comparison of EASI-75) in the model. The percentages, difference in percentages, and 95% confidence interval (CI) of the difference in percentages will be reported. Treatment-by-region interaction will be added to the logistic regression model of the primary and key secondary

variables as a sensitivity analysis. If this interaction is significant at a 2-sided 0.1 level, further inspection will be used to assess whether the interaction is quantitative (i.e., the treatment effect is consistent in direction but not size of effect) or qualitative (the treatment is beneficial for some but not all regions).

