### **5.2.3. Analysis Methods**

The main analysis of categorical efficacy variables and health outcomes variables will use a logistic regression analysis with region, baseline disease severity (IGA) and treatment group in the model. The p-value and 100(1-alpha)% CI for the odds ratio from the logistic regression model are used for primary statistical inference. The difference in percentages and 100(1-alpha)% CI of the difference in percentages using the Newcombe-Wilson without continuity

correction will be reported. The p-value from the Fisher's exact test will also be produced as a secondary analysis.

The main analysis for all continuous efficacy and health outcomes variables will use mixed model repeated measures (MMRM) analysis. The MMRM model will use a restricted maximum likelihood (REML) estimation. The model will include treatment, region, baseline disease severity, visit, and treatment-by-visit-interaction as fixed categorical effects and baseline and baseline-by-visit-interaction as fixed continuous effects. An unstructured (co)variance structure will be used to model the between- and within-patient errors. If this analysis fails to converge, the heterogeneous autoregressive [ARH(1)], followed by the heterogeneous compound symmetry (CSH), followed by the heterogeneous Toeplitz (TOEPH) will be used. The Kenward-Roger method will be used to estimate the degrees of freedom. Type III tests for the least-squares means (LSM) will be used for the statistical comparison. The LSM difference, standard error, p-value and 100(1-alpha)% CI will also be reported.

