### **5.3. Covariate Adjustment**

The randomization to treatment groups at Week 0 (Visit 2) is stratified by disease severity (IGA) and geographic region as described in Section 4.1. Unless otherwise specified, the statistical analysis models will adjust for disease severity and geographical region. When an MMRM analysis is performed, baseline value and baseline-by-visit interactions will be included as covariates.

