### **5.5. Multicenter Studies**

This study will be conducted by multiple investigators at multiple sites internationally. The countries will be categorized into geographic regions, as described in Section 4.2.

For the analysis of the primary endpoint, treatment-by-region interaction will be added to the logistic regression model as a sensitivity analysis and results from this model will be compared to the primary model (without the interaction effect). If the treatment-by-region interaction is significant at a 2-sided  $\alpha$  level of 0.1, the nature of this interaction will be inspected as to whether it is quantitative (ie, the treatment effect is consistent in direction across all regions but not in size of treatment effect) or qualitative (the treatment is beneficial in some but not all regions). If the treatment-by-region interaction effect is found to be quantitative, results from the primary model will be presented. If the treatment-by-region interaction effect is found to be qualitative, further inspection will be used to identify in which regions LY3375880 is found to be more beneficial.

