Descriptive statistics will be provided for each treatment and stratum of a subgroup as outlined, regardless of sample size. The subgroup analyses for categorical outcomes will be performed using logistic regression. The model will include the categorical outcome as the dependent variable and treatment, subgroup, and treatment-by-subgroup interaction as explanatory variables. Missing data will be imputed using NRI (Section 5.4.1). The treatment-by-subgroup interaction comparing treatment groups will be tested at the 0.1 significance level. The p-value from the logistic regression model will be reported for the interaction test. Response counts and percentages will be summarized by treatment for each subgroup category. The difference in percentages and 100(1-alpha)% confidence interval (CI) of the difference in percentages using the Newcombe-Wilson without continuity correction will be reported. The p-value from the Fisher's exact test will also be produced.

Additional subgroup analyses on efficacy may be performed as deemed appropriate and necessary.

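### The subgroup interaction model omits the randomisation strata that the main model carries, so treatment-by-region is tested by two models at 0.10 (a cheap improvement, minor)

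*Protocol*

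**What the plan says.** Randomisation is stratified by IGA (3 v 4) and by Japan against the rest (Protocol 7.2, SAP 4.2). The main model for categorical efficacy outcomes carries both factors. Protocol 10.2.1 describes a "logistic regression analysis with treatment, baseline disease severity (IGA 3 versus 4), geographic region, and, if applicable, baseline scores", and SAP 5.2.3 a "logistic regression analysis with region, baseline disease severity (IGA) and treatment group in the model". SAP 5.3 sets the default: "Unless otherwise specified, the statistical analysis models will adjust for disease severity and geographical region".

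The subgroup model is shorter. Protocol 10.2.7.2 gives three terms: "A logistic regression model with treatment, subgroup, and the interaction of subgroup-by-treatment included as factors will be used". SAP 5.14 agrees: "The model will include the categorical outcome as the dependent variable and treatment, subgroup, and treatment-by-subgroup interaction as explanatory variables". Both use the same threshold: "The subgroup-by-treatment interaction will be tested at the significance level of 0.10" (Protocol) and "The treatment-by-subgroup interaction comparing treatment groups will be tested at the 0.1 significance level" (SAP).

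Region and baseline IGA are themselves listed as subgroups in SAP 5.14. For the primary endpoint, SAP 5.5 separately says that "treatment-by-region interaction will be added to the logistic regression model as a sensitivity analysis", also judged at 0.1. Protocol 10.2.1 plans the same test.

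**The concern.** There are two issues.

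1. The trial balances on IGA and region and adjusts for them in its main model, then leaves them out of the subgroup model without giving a reason. IGA is likely to be prognostic by construction. Entry requires IGA of at least 3 and response requires 0 or 1, so a subject starting at 3 must improve by at least two grades and a subject starting at 4 by at least three. Omitting a prognostic covariate from a logistic model pulls the odds ratios, including the interaction odds ratio, towards 1 and costs power.

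2. Treatment-by-region on the primary endpoint gets two p-values against the same threshold: one from the main model plus interaction (with IGA), one from the subgroup model (without IGA). SAP 5.5 attaches steps to its result: an inspection of whether the interaction is quantitative or qualitative, and a rule on what is then presented. If the two tests fall on opposite sides of 0.10, the plan does not say which one counts.

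**Working it through.** **The plan's own figure.** The documents state power only for the pairwise primary comparison: at least 90% for 36% v 8%, 50 per arm, two-sided Fisher's exact test at 0.05. Exact enumeration gives 91.4% at 50 per arm (90.7% at 49, 89.9% at 48), so that figure reproduces. No power is stated for any interaction test.

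**Terms side by side (primary endpoint).**

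| Analysis | Treatment | IGA | Region | Interaction |
|---|---|---|---|---|
| Main model | yes | yes | yes | none |
| Region sensitivity test (Protocol 10.2.1, SAP 5.5) | yes | yes | yes | treatment-by-region |
| Subgroup model, region row | yes | no | yes | treatment-by-region |
| Subgroup model, IGA row | yes | yes | no | treatment-by-IGA |
| Subgroup model, other rows | yes | no | no | treatment-by-subgroup |

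**Simulation.** From the documents: four arms of 50, 8% placebo and 36% active response, test at 0.10. Assumed, because the documents give no values: IGA 4 share 50%, Japan share 20%, region odds ratio 1.5, an even binary subgroup, a true interaction odds ratio of 6 common to all doses, and IGA odds ratios of 1.5 to 5. The test is the 3-degree-of-freedom likelihood-ratio test of the interaction, run on the same data with and without the missing strata, in 6,000 trials per scenario.

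| Subgroup | IGA odds ratio | Power, strata omitted | Power, strata included | Gain in points (paired SE) | Verdicts differ |
|---|---|---|---|---|---|
| Generic | 1.5 | 36.4% | 37.6% | 1.1 (0.25) | 3.6% |
| Generic | 2 | 35.9% | 37.1% | 1.2 (0.29) | 5.0% |
| Generic | 3 | 34.3% | 37.1% | 2.8 (0.34) | 6.8% |
| Generic | 5 | 32.1% | 37.1% | 5.0 (0.42) | 10.3% |
| Region | 1.5 | 32.2% | 32.7% | 0.5 (0.23) | 3.2% |
| Region | 2 | 30.6% | 31.7% | 1.1 (0.28) | 4.9% |
| Region | 3 | 29.5% | 31.5% | 2.0 (0.35) | 7.5% |
| Region | 5 | 29.0% | 31.9% | 2.9 (0.43) | 11.2% |

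Gains come from unrounded rates. The IGA row, which lacks only region, was not simulated.

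A further set of runs for a generic subgroup gave gains of about 0.5, 2.5 and 4 points at IGA odds ratios of 1.5, 3 and 5. After correction for the actual size of each test, the gain was roughly 1 to 2 points.

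**Under no interaction** (1,500 trials per scenario, Japan share 20% or 40%), both models reject in about 11% to 13.5% of trials against a nominal 10%. Neither is consistently lower.

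**Disagreement between the two region tests.** The runs above do not balance IGA within region. When it is balanced, as joint stratification would tend to do, the tests disagree in 0.5% to 3.6% of trials with no interaction and 1.5% to 9% with interaction odds ratio 6 (IGA odds ratios 2 to 5, Japan 20% or 40%). In those runs the null rejection rate is 9% to 12% without IGA and 12% to 13% with it, so part of the region row's gain is size rather than power.

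**Sparsity.** Expected placebo responders are 0.08 × 50 = 4. With halves of 25, the chance that a given half has none is 0.92^25 = 0.124. The chance that at least one half has none is 1 − (1 − 0.124)² = 0.23.

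**The case against.** The case for leaving the model alone is reasonable. Protocol and SAP agree on it, and the SAP 5.3 default yields wherever a section specifies otherwise, as SAP 5.14 can be read to do. Protocol 10.2.7.2 says the study is not powered for subgroups and treats them as exploratory. The SAP 5.5 test is labelled a sensitivity analysis, so two p-values with different purposes are not a contradiction. With about four placebo responders, a minimal model is defensible, and two more terms do nothing for the sparsity. All of this stands and limits the point to a minor one. It does not supply a reason for the omission or say which region test governs.

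Some stronger readings are tempting but unsupported:

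- A reader might infer that omitting the strata produces spurious findings through chance IGA imbalance. The null rejection rates do not show this. The imbalance is also smaller than a simple binomial calculation suggests: sqrt(2 × 0.25/25) = 0.14 ignores that stratification fixes each arm's overall IGA split. With 25 of 50 at IGA 4 and a subgroup of 25 per arm, the SD is sqrt(2 × 0.25/25 × 25/49) = 0.10, so about 10 to 11 points.
- A reader might infer that these tests decide which subgroups or markers go forward. Protocol 10.2.7.2 says only that a significant interaction will be explored, and SAP 5.14 that its p-value will be reported.
- A reader might take the share of differing verdicts as a measure of harm. Verdicts differ in about 3% of trials even when the strata have no effect, simply because two terms were added.

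**Conclusion.** The point holds as a cheap, minor improvement. The subgroup model omits strata that the main model and the SAP default include, and treatment-by-region on the primary endpoint has two tests at 0.10 with no rule between them.

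The cost is about 0.5 to 5 points of interaction power over assumed IGA odds ratios of 1.5 to 5, with power about 29% to 38% in either case, and less once test size is allowed for. These figures depend on the assumed prognostic strength, Japan share and interaction size, none of which the documents give. Adding the strata does not improve false-positive control, and no primary conclusion changes.

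**What to change.** In SAP 5.14, with Protocol 10.2.7.2 brought into line, state the subgroup model as treatment, baseline IGA (3 v 4), region, subgroup and treatment-by-subgroup, with the duplicate term dropped when the subgroup is IGA or region. State that the SAP 5.5 model is the single treatment-by-region test for the primary endpoint, and that the region row of the subgroup table reports its p-value.

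For EASI75 and Itch NRS, which SAP 5.14 also covers, say whether the baseline score enters. Protocol 10.2.1 adds it where applicable and the SAP 5.2.3 logistic model does not, so the exact match with the region test is assured only for the primary endpoint.

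The downside is two more main-effect terms in sparse data. Name a penalised-likelihood (Firth) fallback and the condition that triggers it, such as separation or non-convergence. If the sponsor prefers the shorter model, a sentence giving the reason and naming the governing region test would also settle the matter.

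The cost is a sentence or two and one changed model statement, with no new data. The choice should be made before anyone making it sees unblinded results.
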